# Primary Endpoints: Results from F-FSPG PET/CT:

- Demonstrate significance accuracy in discrimination of benign from malignant nodules/masses equal to or greater than F-FDG PET/CT, especially for inflammatory/infectious lung nodules, or trend toward significance should additional subjects be enrolled.
- 2. Demonstrate equivalent or superior accuracy for staging of lung cancer compared to F-FDG PET/CT, or trend towards significance should additional subjects be enrolled.

# Sample Size and Study Power

Because our study population will not originate solely from a lung cancer screening trial, it will be "enriched" for high risk of malignancy. Thus, the sample size calculation primarily focuses on the power to detect the minimum clinically important difference in the specificity of F-FDG and F-FSPG tests (19). Accordingly, comparing to F-FDG PET/CT scans, we hypothesize that use of the F-FSPG PET/CT will improve specificity for lung cancer diagnosis in our study population from 40% (F-FDG) to 80% (F-FSPG). We use McNemar's test for paired data to evaluate the specificity for these two methods. We assume the proportion of the discordant pairs is 0.2 and 0.6. A sample size of 37 benign subjects provides 80% power to detect a 40% increase in specificity with a two-sided type 1 error = 5%. Sixty-two subjects will be recruited to take the historic lung cancer prevalence of 0.4 (19) for the referral population to the pulmonary medicine or thoracic surgery services at VUMC for an IPN or lung mass. We will also apply a non-inferiority test to show that the sensitivity of F-FSPG is not worse than the F-FDG. A sample size of 25 cancer patients achieves 82% power at a 5% type 1 error using one-sided equivalence test when the sensitivity of F-FDG is 0.9 (42) and the maximum allowable difference between F-FDG and F-FSPG is 0.2. Thus, we propose to enroll up to 60 subjects to allow for possible dropout such as subjects lost to follow-up or choosing to withdraw from the study before protocol completion.

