#### 5. Enrollment/Randomization

We propose a three (3) year funded prospective cohort with consecutive subject enrollment throughout each year. We will enroll subjects referred to the Oncology, Thoracic Surgery or Pulmonary Medicine Services at Vanderbilt University Medical Center and Tennessee Valley Healthcare System Nashville. We will allow a 2-year follow-up of all subjects to document stability by CT for IPNs that do not have a tissue diagnosis (stability on CT for two years of an IPN or mass is accepted presumptive evidence of benignity). Follow-up will be from the day of the baseline CT, and may be extended later if needed. At VUMC, we see about 750 patients with newly diagnosed IPNs annually, and about 400 patients with newly diagnosed lung cancer. Accordingly, given the high prevalence of granulomatous IPNs in our geographic region, we are well suited to perform the work we have described.

We will perform an analysis to correlate the F-FSPG PET/CT findings with F-FDG PET/CT and the surgical pathology results for the patients who have tissue correlation. Each subject will receive the "standard-of-care" F-FDG PET/CT as indicated for patients at high risk for lung cancer who have an IPN or lung mass meeting our size criteria, and will also receive the investigational F-FSPG PET/CT, with no intervening treatment of the target lesion(s). After enrolling 30 subjects, we will close enrollment but continue the study for data collection and analysis until the funding period ends and/or sufficient follow-up for diagnosis (up to 2 years) has occurred, and report our results in the peer-reviewed literature.

Should we achieve clear statistical superiority of F-FSPG PET/CT over F-FDG PET/CT before that time, we will pursue a larger trial to offer improved benefit of our patients for the diagnosis of IPNs and/or staging of lung cancer (*see* Go/No-Go criteria in Study Design). While 2 years' stability in nodule size is the "gold standard" for CT, well over 90% of cancers demonstrate growth on CT within one year. We will also perform the research outlined in Specific Aim 3 on tissue specimens obtained from our subjects in Specific Aims 1 and 2. If we find significant added value from the use of F-FSPG in either IPNs or lung cancer, we will propose further investigations.

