#### **11. Statistical Considerations**

#### **Study Design**

As we have shown from a large review of patients referred to us for IPNs and lung masses, F-FDG PET/CT has 92% sensitivity but 40% specificity for diagnosis of cancer, primarily due to inflammatory (especially granulomatous) lung nodules in our population. For F-FSPG to have a significant impact, we assume that the sensitivity of F-FSPG will be equal to F-FDG, but that the specificity of F-FSPG for the diagnosis of lung cancer will be 80%. Given the preliminary data we have shown with virtually no F-FSPG uptake in an active granulomatous abscess, we are very optimistic that our approach could succeed.

Our preliminary proposed investigation will include 30 subjects who had both PET scans done FDG and FSPG of patients meeting enrollment criteria and referred from the VUMC Pulmonary Medicine or Thoracic Surgical Oncology services. We will include those IPNs or lung cancers discovered *via* lung cancer screening or referred for a non-screened discovered IPN or cancer. If our preliminary data are encouraging, we will seek additional funding to enroll more to achieve statistical significance. However, we predict that we will need to extend the study to a total of 70 subjects completing a study to achieve significance. Our plans for the additional funding will be to approach the current IP holder (Piramal Life Sciences) as well as to apply for extra-mural funding with initial data from our initial subjects.

**Go/No-Go criteria:** To verify that data collected in this pilot imaging study supports proceeding to a larger efficacy trial, clear Go/No-Go criteria, which will be assessed at the end of enrollment and data analysis, have been established for each aim, and include:

A. Aim  $1 - {}^{18}$ F-FSPG PET/CT has equal sensitivity to  ${}^{18}$ -FDG PET/CT, with  $\ge 50\%$  specificity, compared to the proven 40% specificity of  ${}^{18}$ F-FDG PET/CT, for the diagnosis of indeterminate lung nodules, in our area with high endemic rates of fungal nodules.

B. Aim 2 –  $^{18}$ F-FSPG PET/CT is at least equivalent in overall accuracy to  $^{18}$ F-FDG PET/CT for staging of lung cancer.

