# **Data Analysis**

As part of our "go/no go" analysis as initial proof of principle, we plan to enroll 30 subjects initially with IPNs or newly discovered lung masses, to determine if this initial enrollment will demonstrate a trend toward significance in accuracy for diagnosis of IPNs or lung masses. This will be an initial, "proof of principle" investigation. If not, we will consider other imaging probes. However, if we do see a trend of significance, we plan on 70 subjects to complete a study.

We will not know at time of enrollment if the subject has a benign or malignant IPN or mass. Historically, we have a 40% prevalence of cancer in our referral base, which, heretofore, is not a "screened" population. Thus, with 70 subjects completing a study, we expect that, after tissue confirmation or adequate clinical follow-up to establish benignity is established, to have about 42 subjects with benign nodules and 28 with cancer. The analysis of Specific Aim 1 will focus on the F-FSPG PET/CT's ability to discriminate up-front benign from malignant lung nodules/masses in all subjects. Analysis of Specific Aim 2 will then focus on analysis of known/confirmed lung cancers. Specific Aim 3 analysis will correlate the biomarker findings as described elsewhere in the Project Narrative with the findings of Specific Aims 1 and 2.

Sensitivity, specificity, overall accuracy and ROC curves will be generated and compared for both F-FDG and F-FSPG tests. Wilcoxon rank-sum or Kruskal-Wallis tests will be applied for the group comparisons of immunohistochemical staining (CD44 and  $x_c^-$  expression levels, Specific Aim 3) and the biodistribution characteristics of F-FDG and F-FSPG tests (Specific Aims 1 & 2). The demographic information such as age, smoking status/pack-year history will be tabulated. Descriptive statistics, including means, standard deviations, and ranges for continuous parameters (uptake expressed in SUVmax, SUVmean, SUVpeak) normalized to lean body mass and body weight, and ratios of these uptake values to cardiac blood pool and normal lung. as well as percentages and frequencies for categorical parameters, will be presented.

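### The enrolment cap of 60, said to allow for dropout, is below the 62 evaluable subjects the same paragraph requires, so it contains no dropout allowance

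*Combined protocol and SAP*

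**What the plan says.** The figures at issue are all in one paragraph of the combined protocol and SAP, Section 11, Sample Size and Study Power.

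- Specificity: "A sample size of 37 benign subjects provides 80% power to detect a 40% increase in specificity", using McNemar's test at a two-sided 5% level with discordant proportions of 0.2 and 0.6.
- Total: "Sixty-two subjects will be recruited to take the historic lung cancer prevalence of 0.4".
- Sensitivity: "A sample size of 25 cancer patients achieves 82% power", for a one-sided 5% test with a margin of 0.2 and an FDG sensitivity of 0.9.
- Conclusion: "Thus, we propose to enroll up to 60 subjects to allow for possible dropout". No dropout rate is given here or anywhere else.

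Other sections give other totals.

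- Section 5: "After enrolling 30 subjects, we will close enrollment but continue the study for data collection and analysis".
- Section 7, Imaging Protocol: the rule on the interval between the two scans is attached to the first 60 people enrolled. Later in the same section, a larger trial of 40 additional subjects follows if superiority is established.
- Section 11, Study Design: "If our preliminary data are encouraging, we will seek additional funding to enroll more to achieve statistical significance", and the prediction that the team will need to "extend the study to a total of 70 subjects completing a study to achieve significance".
- Section 11, Data Analysis: "if we do see a trend of significance, we plan on 70 subjects to complete a study", with an expected 42 benign subjects and 28 cancers.

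**The concern.** A dropout allowance takes the number of evaluable subjects needed and raises it. Here the number needed is 62 and the figure offered as the allowance is 60. The step goes the wrong way, so the cap cannot do what the sentence says it does.

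Loss is a realistic prospect in this design. A nodule without tissue can be called benign only after stability for up to two years, or after shrinkage or resolution, on CT. Subjects lost before then would come mainly from the benign group, and the sample size calculation is built mainly on that group. The stated powers of 80% and 82% belong to 37 and 25 evaluable subjects. A reader who takes 60 as already protected against loss would credit the study with power that the figure does not provide.

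A second problem is that the powered stage has no single size: 60 enrolled, 62 recruited and 70 completing all appear, and 60 enrolled cannot yield 70 completers.

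**Working it through.** **Inputs**, all from Section 11: discordant proportions 0.6 and 0.2 (sum 0.8, difference 0.4); two-sided 5% level; 80% power; cancer prevalence 0.4, so benign fraction 0.6; 25 cancers required; cap of 60; conditional target of 70 completers. Dropout rates below are assumptions.

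**1. The plan's benign requirement reproduces.**

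n = (1.96·√0.8 + 0.8416·√(0.8 − 0.4²))² / 0.4² = 36.8, rounded up to 37.

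**2. The plan's 62 reproduces, with no dropout term.**

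37/0.6 = 61.7, rounded up to 62. Also 37 + 25 = 62, although 62 × 0.4 = 24.8 expected cancers, just under 25.

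**3. What 60 gives with no loss.**

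60 × 0.6 = 36 benign and 60 × 0.4 = 24 cancers, each one short. Since 37 + 25 = 62 > 60, no other split meets both requirements.

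**4. Specificity power.**

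Power = Φ[(0.4·√n − 1.96·√s) / √(s − 0.16)], where s is the total discordance and n the number of benign subjects. Benign counts after loss: 60 × 0.9 × 0.6 = 32.4, about 32; 60 × 0.8 × 0.6 = 28.8, about 29.

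| Case | Benign n | 0.6/0.2 (plan) | 0.5/0.1 (assumed) | 0.48/0.08 (independent readings) |
|---|---|---|---|---|
| Plan's requirement | 37 | 80.2% | 91.6% | 93.7% |
| 60 enrolled, no loss | 36 | 79.1% | 90.8% | 93.0% |
| 60 enrolled, assumed 10% loss | 32 | 73.8% | 86.9% | 89.6% |
| 60 enrolled, assumed 20% loss | 29 | 69.2% | 83.1% | 86.1% |
| 70 completers | 42 | 85.3% | 94.7% | 96.2% |

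With specificities of 40% and 80%, the larger discordant cell cannot exceed 1 − 0.4 = 0.6, so the smaller cannot exceed 0.6 − 0.4 = 0.2. The plan's total of 0.8 is therefore the maximum possible, and its column is the least favourable. The independence column uses 0.8 × 0.6 = 0.48 and 0.2 × 0.4 = 0.08.

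**5. Sensitivity power.**

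For a paired test with equal sensitivities, power = Φ[0.2/√(s/n) − 1.645]. With s = 0.15 this gives 82.6% at 25 cancers and 81.2% at 24. With s = 0.18 it gives 76.2% and 74.7%. The plan states no discordance for this comparison, so its 82% cannot be carried over to 24 cancers without stating one.

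**The case against.** The strongest reply is that little depends on this. The gap is two subjects and about 1 point of power. The larger falls in power need dropout rates that the documents do not give, and they use the least favourable discordance. Under independent readings, power is still 86.1% at 20% loss. The protocol also acts to limit loss: inclusion criterion 6 requires agreement to biopsy or 24 months of follow-up, exclusion criterion 5 is aimed at preventing lost CT follow-up, and Section 5 lets follow-up be extended. The committed first stage is 30 subjects, and its Aim 1 Go rule uses observed sensitivity and specificity rather than this calculation. The later target of 70 completers (42 benign, 28 cancers) exceeds both requirements.

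Much of this stands, and it limits the size of the point. It does not repair the sentence. The follow-up measures supply no number. The 70 depends on first-stage results and, in Study Design, on further funding. The power paragraph does not mention it, and 60 enrolled cannot produce it.

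Two stronger readings are tempting. A reader might infer that the 30 in Section 5 contradicts the 60. The documents do not require that: 60 is a maximum, and Study Design and Data Analysis present 30 as an initial stage. Only the wording about closing enrolment needs adjusting. A reader might also infer that the study is seriously underpowered. That would need both a substantial loss, for which no rate is given, and discordance at its maximum.

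**Conclusion.** The statement is wrong as written, and the arithmetic needs nothing outside the paragraph: 60 is less than 37 + 25, so it holds no allowance for dropout. The enrolment figure for the powered stage is also unsettled between 60, 62 and 70.

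The certain effect is small: one benign subject and one cancer short in expectation, and 79.1% specificity power instead of 80.2% under the plan's own discordance. Anything larger is conditional on assumptions: about 74% at 10% loss, and above 80% throughout the range shown if discordance is milder. The point should be corrected because the protocol makes a specific claim of protection against loss that its figures do not support, and because correcting it is cheap.

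**What to change.** 1. Delete the claim that 60 allows for dropout, or state the dropout rate on which the enrolment figure rests.
2. Give one enrolment figure and one completer figure for each stage. Make Section 5, Section 7 (both the reference to the first 60 enrolled and the additional 40) and the Study Design, Sample Size and Data Analysis parts of Section 11 agree. Reword the closing of enrolment after 30 so that it plainly ends the first stage.
3. Then take one of two routes.
   - *Keep 60.* State the expected counts as 36 benign and 24 cancers and the specificity power as about 79% before any loss. Recompute the sensitivity power for 24 cancers with its discordance assumption stated, in place of 82%.
   - *Use the existing 70 completers as the powered stage.* Tie the power statement to about 42 benign subjects (85% under 0.6/0.2) and 28 cancers, with the sensitivity power recomputed likewise. Give enrolment as 70/(1 − d) for a stated rate d. For illustration, 70/0.9 = 77.8, so 78 at 10%; 70/0.8 = 87.5, so 88 at 20%.

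These counts are expectations. At prevalence 0.4, the binomial probability that 70 evaluable subjects include at least 37 benign and at least 25 cancers is about 71%; at 63, the smallest total at which both are expected, it is about 20%. Neither total should be described as securing both groups.

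Steps 1 and 2 and the first route are wording and a short recalculation. The second route keeps a completer target that the plan already has; its added cost is the subjects and scans enrolled beyond 70 to cover the stated loss (8 at 10%, 18 at 20%).

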# **Data Analysis**

As part of our "go/no go" analysis as initial proof of principle, we plan to enroll 30 subjects initially with IPNs or newly discovered lung masses, to determine if this initial enrollment will demonstrate a trend toward significance in accuracy for diagnosis of IPNs or lung masses. This will be an initial, "proof of principle" investigation. If not, we will consider other imaging probes. However, if we do see a trend of significance, we plan on 70 subjects to complete a study.

We will not know at time of enrollment if the subject has a benign or malignant IPN or mass. Historically, we have a 40% prevalence of cancer in our referral base, which, heretofore, is not a "screened" population. Thus, with 70 subjects completing a study, we expect that, after tissue confirmation or adequate clinical follow-up to establish benignity is established, to have about 42 subjects with benign nodules and 28 with cancer. The analysis of Specific Aim 1 will focus on the F-FSPG PET/CT's ability to discriminate up-front benign from malignant lung nodules/masses in all subjects. Analysis of Specific Aim 2 will then focus on analysis of known/confirmed lung cancers. Specific Aim 3 analysis will correlate the biomarker findings as described elsewhere in the Project Narrative with the findings of Specific Aims 1 and 2.

Sensitivity, specificity, overall accuracy and ROC curves will be generated and compared for both F-FDG and F-FSPG tests. Wilcoxon rank-sum or Kruskal-Wallis tests will be applied for the group comparisons of immunohistochemical staining (CD44 and  $x_c^-$  expression levels, Specific Aim 3) and the biodistribution characteristics of F-FDG and F-FSPG tests (Specific Aims 1 & 2). The demographic information such as age, smoking status/pack-year history will be tabulated. Descriptive statistics, including means, standard deviations, and ranges for continuous parameters (uptake expressed in SUVmax, SUVmean, SUVpeak) normalized to lean body mass and body weight, and ratios of these uptake values to cardiac blood pool and normal lung. as well as percentages and frequencies for categorical parameters, will be presented.

# **12.** Privacy / Confidentiality

All reasonable efforts will be made to keep patient health information private and confidential. To satisfy the reporting requirements of regulatory bodies and study sponsors, [name] and the study team will report study results as needed to the National Institutes of Health (NIH), US Food and Drug Administration (FDA), Vanderbilt Institutional Review Board (IRB), or other state and federal regulatory bodies. In reporting results for publication, all medical information will be de-identified in compliance with HIPPA regulations. Reasonable effort will also be made to keep personal information in research records private and confidential. Access to coded research data will be limited to key study personnel. Signed consent forms will be maintained in a locked file cabinet in the Vanderbilt Clinical Trials office.

# 13. Follow-up and Record Retention

Study results will be retained in the research record for at least six years after the study is completed. At that time, the research information not already in the patient's medical record will be stored in a locked file cabinet in the Vanderbilt Clinical Trials office. Any research information in the medical record will be kept indefinitely.

Following closure of the study, each participating center will maintain a copy of all site study records in a safe and secure location. The Coordinating Center will inform the investigator at each site at such time that the records may be destroyed.

Study Procedure Calendar (2-year follow-up by CT only needed for subjects without a definitive diagnosis of the nodule or mass by biopsy)

	Year 0: Study Initiation	Year 1	Year 2
Initial Visit	x		
Consent	х		
Finger-stick Glucose (in PET/CT lab)	x		
Blood draw (for pregancy test for female subjects of childbearing potential only)	x		
Chest CT Review	SOC	SOC	SOC
 F-FSPG PET/CT	х		
 F-FDG PET/CT	SOC		
Adverse Event Follow- up	Performed day after  F-FSPG scan as described		

